1.0 Introduction

1.1 Study Objectives:

The purpose of this study is to evaluate the hypothesis that use of atherosclerosis imaging to set targets for cholesterol lowering therapy will result in greater regression of atherosclerosis than standard therapy.

The primary efficacy endpoint of this study is the wall volume of the internal carotid arteries as measured by magnetic resonance imaging.

Secondary endpoints are

- A. Arterial stenosis and plaque volume measured by coronary MDCTA
- B. Dosage of statin medications required to achieve LDL targets.
- C. Combined incidence of stroke, nonfatal MI, myocardial revascularization, hospitalization for unstable angina or heart failure and death.
- D. FDG plaque uptake within the carotid and coronary arteries.

E. Reproducibility of arterial stenosis and plaque volume measured by MDCTA.

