Previous studies including our own have demonstrated the ability of lipidmodifying drugs, specifically HMG-CoA reductase inhibitors, to induce measurable regression of atherosclerosis. We propose to compare two different approaches to achieve atherosclerotic plaque regression and stabilization using the primary endpoints of carotid atherosclerotic plaque volume and composition defined by MRI. We also propose to measure coronary plaque regression defined by 320 detector row CT angiography, in order to evaluate whether carotid and coronary plaque regression occur in parallel. Finally, we propose to compare the benefit of these two lipid lowering strategies on clinical CV events. In order to achieve all of these objectives, state-of-the-art MRI techniques refined from our previous trial in similar population will be employed to quantify atherosclerotic plaque volume and composition in the carotid arteries, and to measure carotid arterial distensibility and pulse wave velocity. The newest generation of 320 detector CT scanners will be used to measure atheroma volume in the coronary arteries and differentiate between calcified and non-calcified lipid-rich and/or fibrous lesions. We hypothesize that guidance of lipid modifying therapy using imaging assessment of atherosclerosis to intensify or reduce lipid lowering therapy in patients with respectively greater or lesser plague volume at the baseline examination will result in greater plague regression and stabilization than standard NCEP guided therapy with the same or superior safety and/or treatment adherence profiles.

In a subset of individuals we plan to look at plaque inflammation using FDG PET. Molecular imaging compliments traditional anatomical imaging

approaches that identify plaque structure and composition.

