It is widely postulated in the literature that ¹⁸F-fluorodeoxyglucose (FDG) imaging can improve risk assessment and prognostication through the identification of high-risk "vulnerable" plaques, plaques that demonstrate heightened inflammation, neovascularization or apoptosis. The primary target is the carotid and coronary arteries, imaging will also include the ascending and descending aorta, and the iliac arteries. Successful FDG PET imaging has been performed in large vascular beds, including the carotid arteries, and recent preliminary reports suggest the potential for noninvasive coronary plaque imaging. The advantage of nuclear imaging is that multiple vascular beds can be imaged with a single radionuclear isotope administration.

In a subset of 60 individuals we plan to study the reproducibility of arterial stenosis and plaque volume as measured by MDCTA.

At present, there is no available data on the reproducibility of 320 detector row MDCT for measuring arterial stenosis and plaque volume. This data will allow investigators to determine whether measured changes in stenoses and plaque morphology exceed that expected from the limits of measurement error in CTA and thus make the results of ongoing trials more reliable.

Consistent with such objectives, our specific aims are:

1st Aim

To examine whether image guided lipid lowering therapy is superior to NCEP guided therapy in promoting carotid atherosclerotic plaque regression and stabilization.

2rd Aim

To investigate whether the observed change in carotid atherosclerosis volume measured by MR, parallels observed change in coronary atherosclerosis volume measured by MDCT angiography.

3rd Aim

To examine whether MRI guided plaque regression and stabilization produces greater reduction in clinical CV events than standard NCEP guided therapy.

4th Aim

To examine the statin dosages required to promote plaque regression and stabilization differ between conventional and image guided strategies.

5th Aim

To investigate whether FDG PET activity predicts carotid morphological plaque regression and stabilization in both the carotid and coronary arteries and compare the efficacy of PET based prediction with MRI.

6th Aim

To correlate FDG uptake in the carotid, coronary, aortic, and iliac arteries with absolute values and changes in hematological biomarkers of vascular inflammation, thrombosis and atheroprotection at and between each time point.

7th Aim

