Allowable statin compounds and maximum dosages are:

compound	maximum allowable dose	comments
atorvastatin	80 mg /day	
fluvastatin	80 mg/ day	
lovastatin		
(immed. release)	80mg/day	

extended release	60 mg/day	
pravastatin	80 mg/ day	either 40 mg immediate
		release twice daily OR 80 mg
		extended release once daily
rosuvastatin	40 mg/ day	
simvastatin	80 mg/day	

Subjects assigned to both arms of the study will undergo carotid MR for plaque evaluation at baseline, 12 and 24 months of followup. 320 detector row MDCT angiography will be performed at baseline and 24 months. Only unscheduled visits for evaluation of drug toxicity or potential clinical events will not coincide with intervention visits.

Carotid MRI

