Informed written consent will be obtained for each participant. Exclusion criteria will include contraindications for CT imaging or contrast administration and arrhythmia.

[figure not shown]
Coronary calcification

Coronary calcification will be measured by the Agatston⁽¹⁰⁾ method, correcting lesion area by the density of calcification in the lesion. A density independent volume score will also be calculated. Total coronary artery calcium scores will be generated by summing the values from the left main, left anterior descending, left circumflex and right coronary arteries. Readers will be blinded to subject identity.

Plaque quantification

Raw data will be reconstructed at 0.5 mm slice-thickness by a multisegment reconstruction algorithm. The baseline axial MDCT images with adequate reconstruction phase will be post processed and analyzed by commercial software (Sure Plaque, Toshiba Medical Systems). Lumen and wall boundaries of target vessels will be semi-automatically detected on cross sectional images. Under the guide of stretched multiplanar reconstructed image (SPR), two experienced readers will review and edit lumen and outer wall contours of coronary segments of the left anterior descending coronary artery (LAD), left circumflex coronary artery (LCX) and right coronary artery (RCA) from ostium to vessel diameter > 2.0mm from cross sectional image by each 1.0 mm in length. Segments with artifact, blur, or stent will be excluded. Volume estimates are obtained by multiplying cross sectional area by slice thickness. Coronary wall volume is computed by subtracting lumen volume from vessel volume.

To quantify coronary lumen volume, vessel wall volume, and total vessel volume by MDCTA we will obtain three indices from MDCTA analysis of the lumen and vessel borders: 1) coronary lumen volume/ vessel volume (LV/VV), 2) coronary wall volume/ vessel volume (WV/VV) and 3) coronary wall volume/ lumen volume (WV/LV) (Fig. 1). The greatest value for all indices obtained for each vessel and patient will be recorded.

T = wall thickness LV= lumen volume VV = vessel volume

Outer contour – volume circumscribed by the outer border of the vessel wall (mm³)

Lumen – volume circumscribed by the inner border of the vessel wall (mm^3)

Wall volume = Outer contour volume – lumen volume (mm³)

PET Substudy

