Standard statistical methods⁽²⁴⁾ will be used to describe the demographic characteristics, clinical manifestations and basic summary statistics as rates or means (medians). Confidence intervals will also be computed. If necessary, permutation methods⁽²⁶⁾ will be employed.

For Hypotheses 1, 2, and 4:

Linear mixed (random-effects) models⁽²⁷⁾ will be used to study differential changes over time in plaque size and composition and drug dosage between the two treatments. Each model will include main effects of time from baseline and treatment, with interactions tested separately. To decide on the correlation structure for these models, variation due to random effects, serial correlation and measurement error will be examined using the variogram. These models will also be used to isolate specific comparisons of outcome variables at specific time points between the two arms. The required assumptions of normally distributed errors and random effects can be checked by an analysis of standardized residuals. which are now available for the mixed model. In the event that the assumptions are not satisfied, usually because of skewed error distributions, data transformations from the Box-Cox power family will be considered. The most commonly used member of this family is the logarithmic transformation, which usually corrects a problem with right skewness.

For Hypothesis 3:

For the time-to-event data, both the Kaplan-Meier estimate and the Cox proportional hazards model will be employed. The primary analysis will compare the two treatments using a log-rank test. Secondary analyses will use the Cox model to include adjustment for covariates. A non-parametric proportional hazards model will also be used to explore possible transformations of independent variables in the models⁽²⁸⁾.

For Hypothesis 5, 6, and 7:

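### Recording the greatest LV/VV takes that index from the least diseased coronary vessel or site, while WV/VV and WV/LV come from the most diseased

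*Combined protocol and SAP*

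**What the plan says.** Section 1.3 Design, under Plaque quantification, has readers contour lumen and outer wall in the LAD, LCX and RCA. It states that "Coronary wall volume is computed by subtracting lumen volume from vessel volume" and defines three ratios: LV/VV, WV/VV and WV/LV. The summary rule follows: "The greatest value for all indices obtained for each vessel and patient will be recorded". LV/VV is not excepted.

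The uses of coronary CT are set out elsewhere:

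- Section 1.1 lists secondary endpoint A as "Arterial stenosis and plaque volume measured by coronary MDCTA".
- Section 1.2 says "We also propose to measure coronary plaque regression defined by 320 detector row CT angiography", and the second aim asks whether carotid change "parallels observed change in coronary atherosclerosis volume measured by MDCT angiography".
- On timing, Section 1.3 states that "320 detector row MDCT angiography will be performed at baseline and 24 months".
- Section 6.0 plans linear mixed models for "differential changes over time in plaque size and composition and drug dosage between the two treatments". It does not say which coronary index is analysed, or whether at vessel or patient level.

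**The concern.** The three ratios do not point the same way. A high WV/VV or WV/LV means much wall relative to vessel or lumen; a high LV/VV means little. One rule that takes the greatest of each therefore summarises disease at its worst for two indices and at its mildest for the third. Section 1.3 (CT image analysis) otherwise focuses on the worst lesion in each segment, so the LV/VV summary runs against the protocol's own approach.

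If the recorded LV/VV were used to judge coronary change, it could stay flat while the diseased vessel improves, or worsen while WV/VV improves. A second issue arises for all three indices if a patient-level maximum is compared between scans: nothing ties the month-24 maximum to the vessel that gave the baseline maximum. Segments with artifact, blur or a stent are also excluded, which can change the vessel or site that supplies it.

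**Working it through.** The plan gives no figure to reproduce here. The check is algebra on its definitions, followed by illustrations. **All wall fractions below are assumptions; the documents give none.**

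**Step 1: identities.** Write w = WV/VV. From WV = VV − LV (Section 1.3):

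- LV/VV = 1 − w, which falls as w rises.
- WV/LV = w / (1 − w), which rises with w.

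Hence max(LV/VV) = 1 − min(w), while max(WV/VV) and max(WV/LV) both occur at max(w). In 100,000 random three-vessel patients (w uniform on 0.2 to 0.8), the greatest LV/VV came from the vessel with the smallest WV/VV in 100%. The greatest WV/VV and WV/LV shared a vessel in 100%, and the greatest LV/VV and WV/VV in 0%.

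**Step 2: one assumed patient at baseline.**

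| Vessel | WV/VV | LV/VV | WV/LV |
|---|---|---|---|
| A | 0.40 | 0.60 | 0.40/0.60 = 0.67 |
| B | 0.55 | 0.45 | 0.55/0.45 = 1.22 |
| C | 0.70 | 0.30 | 0.70/0.30 = 2.33 |
| Recorded | 0.70 (C) | 0.60 (A) | 2.33 (C) |

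The recorded WV/VV and LV/VV sum to 1.30; within any one vessel they sum to 1.00.

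**Step 3: the same patient at month 24.**

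| Change | max WV/VV | max LV/VV | min LV/VV |
|---|---|---|---|
| C falls to 0.55 only | 0.70 → 0.55 | 0.60 → 0.60 | 0.30 → 0.45 |
| All vessels fall 10% (0.36, 0.495, 0.63) | 0.70 → 0.63 | 0.60 → 0.64 | 0.30 → 0.37 |
| C falls to 0.55, A rises to 0.45 | 0.70 → 0.55 | 0.60 → 0.55 | 0.30 → 0.45 |

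In the first row the recorded LV/VV does not see the regression. In the second it does. In the third it worsens while WV/VV improves. The smallest LV/VV agrees with WV/VV in every row.

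**Step 4: averages by simulation** (200,000 patients per scenario, three independent vessels, w with assumed mean 0.50 and SD 0.08, limited to 0.2 to 0.8).

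| Scenario | Mean change, max WV/VV | Mean change, max LV/VV | max LV/VV unchanged |
|---|---|---|---|
| Worst vessel only, w lower by 0.05 | −0.038 | +0.002 | 90% of patients |
| All vessels, w lower by 10% | −0.057 | +0.043 | 0% |

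**Step 5: vessel switching.** In the first scenario of Step 4 the worst vessel fell by 0.05, but its recorded maximum fell by only 0.038 on average, because another vessel sometimes became the worst. In the Step 2 patient, if C fell from 0.70 to 0.50, the month-24 maximum would be B at 0.55. The recorded change is −0.15, against −0.20 in C itself.

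**The case against.** The strongest reply is that little depends on this ratio. A reader might infer that LV/VV carries secondary endpoint A and the second aim. The documents do not say so: both are worded as stenosis, plaque volume or atherosclerosis volume. Wall volume is also computed in mm³, and Section 6.0 does not make LV/VV an analysed variable. WV/VV is recorded in the right direction and LV/VV is only its complement. This stands, and it limits the consequence.

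A reader might also infer that the recorded LV/VV cannot show regression. That is too strong. It rises whenever the least diseased vessel improves, and statin treatment is systemic, so the worst-vessel-only scenario is the one least favourable to it. Nor can all three indices conflict: WV/LV increases with WV/VV, so only LV/VV can diverge.

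Finally, the rule covers both vessel and patient and can be read in more than one way. If one whole-vessel ratio is kept per vessel at each scan, same-vessel change is available and only the patient-level summary is affected. If the maximum is taken over sites within a vessel, the greatest LV/VV is the healthiest site of each vessel, and the direction error remains. Vessel switching therefore matters only if the patient-level maximum is what is analysed. A worst-vessel summary is in itself a legitimate choice for WV/VV and WV/LV; preferring totals is partly a matter of design.

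None of this removes the direction error. It is a stated rule that contradicts the protocol's own definitions, not a missing detail.

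**Conclusion.** The point holds as a direction error in one of three coronary summary indices. That the greatest LV/VV reflects the least diseased vessel or site, and the other two maxima the most diseased, follows exactly from the protocol's definitions and needs no assumption.

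The size of the effect does rest on assumed wall fractions. Under them, the patient-level LV/VV is unchanged in about 90% of patients when only the worst vessel regresses. It captures +0.043 when regression is diffuse, against −0.057 for WV/VV. Real data would fall at or between these patterns, or show mixed change in which the two indices disagree.

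The primary endpoint (carotid wall volume by MRI) is untouched, and the named coronary endpoint can still be analysed from stenosis and wall volume. The correction is worth making because it costs almost nothing, and because Section 6.0 leaves the coronary index and level open.

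**What to change.** - **Direction.** Record the smallest LV/VV, which equals 1 − max(WV/VV) and points to the same vessel as the other two indices. Alternatively, drop LV/VV as the complement of WV/VV.
- **Change over time.** If a patient-level maximum is used from baseline to month 24, take the month-24 value from the vessel that supplied the baseline value. Otherwise use the per-vessel values, or wall and vessel volumes summed over LAD, LCX and RCA for segments readable at both scans. A vessel chosen for its high baseline value will tend to read lower on repeat in both arms. The comparison between arms stays fair, but the change within one arm should not be read as regression alone.
- **Specification.** State in Section 6.0 which coronary index is analysed and at which level.

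The cost is a few sentences in the analysis plan and a recalculation from volumes already measured, with no new scan, visit or reading. Section 7.4 reports that the study moved to data analysis only in January 2017. The decision should therefore be dated and, if still possible, made before these indices are compared by arm.

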Coronary arterial imaging will be performed during a 4-5 ml/sec intravenous iodinated contrast (ISOVUE[®]-370) infusion using the following parameters: If heart rate is < 66 bpm prospective ECG gating at 70-80% of one R-R interval, X-ray exposure time ranges from 0.423 - 0.350 sec (depending on heart rate). If heart rate is ≥ 66 bpm prospective ECG gating at 40-80% of two R-R intervals, X-ray exposure time ranges from 1.174 sec - 0.714 sec (depending on heart rate) tube voltage = 120kV, tube current = 300 -580 mA depending on BMI and gender, gantry rotation speed = 0.35 or 0.375 seconds, slice thickness = 0.5 mm, rows = 256-320, range = 128-160 mm. The automated bolus tracking feature will be used to judge contrast bolus arrival and optimize image quality.

The estimated radiation dose for the entire cardiac computed protocol (Calcium scoring (1.5 mSv) + Coronary arterial imaging (3-9 mSv) is 4.5 mSv to 10.5 mSv depending on patient heart rate, BMI, and gender. Betablockers will be used to control the heart rate and thus maintain the radiation dose as low as reasonably achievable. Depending on patient size, a maximum of 2 ml/kg iodinated contrast will be used up to a maximum of 130 ml.

Beta Blockade

In order to optimize image quality by reducing cardiac motion, participants will receive beta blockade on the day of the scan. Participants will have heart rate and blood pressure measured, and will be assessed for contraindications to beta blockade (bradycardia, heart block, active wheezing, history of adverse reaction).

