Since the approach to pre-scan beta-blockade is unique to the individual participant, the supervising physician customizes the dose on an individual subject to achieve a goal heart rate of less than 60 beats per minute. A net dose of metoprolol 25-200 mg or atenolol 50-100 mg or diltiazem 90-360 mg will be administered orally potentially in divided doses over a period of approximately 1-2 hours titrated to achieve a heart rate less than 60 beats per minute. In addition, metoprolol or diltiazem 5-30 mg intravenously may be administered in divided doses at the judgment of the supervising physician if heart rate is not adequately controlled and the subject appears capable of tolerating the additional medication. Vital signs will be obtained and documented following metoprolol administration. If at any time the heart rate is <50 bpm and/or the systolic BP is <100, the supervising physician will be notified. All participants will be assessed ofr symptoms of bradycardia, hypotension and orthostasis after scan completion.

Nitrate therapy

The use of short acting nitrates (i.e. sublingual nitroglycerine) just prior to MDCT is required for patients with systolic blood pressure >110mmHg to allow for accurate assessment of the degree of coronary artery stenosis, reduce vasospasm and to standardize vasomotor tone. Potential contraindications to nitroglycerine use should be reviewed prior to administration (known allergy or severe intolerance, critical aortic stenosis, pre-existing hypotension). If the patient cannot receive nitroglycerine (due to intolerance, borderline blood pressure, investigator judgment), the patient may still proceed with the study. Known risks of nitroglycerine use include headache, reduction in blood pressure, hypotension.

CT image analysis

CT angiogram images will be reconstructed and post-processed on a separate workstation using Vitrea (Vital Images, Inc) software. The coronary tree will be segmented for analysis using a 16 segment AHA model according to the CORE-64 protocol ⁽⁹⁾. Vessels larger than 1.5 mm in luminal diameter will be analyzed. The worst lesion per segment will be assessed. Luminal stenosis will be measured using semi-automated software. The spatial volume contained within the visible external wall of the vessel and the volume of the vessel lumen will be measured. A standardized under-patient phantom will be included in each scan to permit between-scan correction of density measurements.

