A subgroup of 60 patients will be recruited to participate in PET scanning which will be performed twice, once at study initiation and after 6 months of trial-directed statin therapy.

Information including cardiovascular risk factors and other medication, including anti-inflammatory drugs, use will be collected. The total cholesterol and LDL levels and the dosage of statins required to achieve that target will be recorded.

Inclusion Criteria:

Participants who are not participating in the CT Reproducibility study are eligible.

Exclusion Criteria:

Patients who are unable or unwilling to comply with the physical activity restrictions or fast for 12 hours prior to FDG PET scanning will be excluded. Due to the need for dietary manipulation and the maintenance of strict glycemic control we will exclude diabetic patients from our initial study sample. Blood glucose measurements before injection must be within normal limits, less than 200 mg/dL (11 mmol/L).

Hematological Biomarkers Markers:

Blood tests for inflammatory markers will be incorporated into the baseline and 6 month blood draws. Standard investigations will include C-reactive protein, matrix metalloproteinase -3 and -9, interleukin-18, cathepsin K, fibrinogen, adiponectin, and plasminogen activator.¹²⁻¹³ A tube of blood will be stored at -70°C for testing of further markers defined at a later date.

FDG PET Preparation:

Study subjects will be asked to fast for 12 hours prior to PET scan. On the morning of the PET study, a low carbohydrate meal will be provided to study participants. Patients will be asked to avoid exercise 24 hours prior to scanning.

Carotid and Cardiac FDG PET Imaging Technique: On the morning of the scan, Metoprolol 50 - 100 mg PO will be administered to slow the heart rate and optimize the acquisition of diastole.¹

The dose of FDG administered, duration between FDG injection and PET image acquisition, and the method of quantification of FDG uptake will be standardized.¹⁵ The injected dose of 18F-fluorodeoxyglucose will be 5.2 MBq/kg (140 mCi/kg) of lean body mass to a maximum of 12.5 mCi.

Patients will be kept resting comfortably in a semi-dark room. Scanning will be initiated after 90 minutes.¹⁶⁻²⁰ Typically, extended time imaging will be performed of the coronary and carotid beds first, followed by a 5 - 15 minute break and imaging of the remainder of the body.

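### Metoprolol before each PET scan is ordered without stated safety checks, and at month 6 no other part of the protocol clearly supplies a same-day check

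*Combined protocol and SAP*

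**What the plan says.** Section 1.3, PET Substudy, plans two FDG PET scans, at study start and after 6 months, in a subgroup of 60. Under the imaging technique it says: "On the morning of the scan, Metoprolol 50 - 100 mg PO will be administered to slow the heart rate". The stated purpose is better acquisition of diastole. The PET text attaches no condition to the dose.

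Beta blockade has its own subheading in the part of section 1.3 on coronary CT angiography, between the CT acquisition settings and the CT image analysis. It opens: "In order to optimize image quality by reducing cardiac motion, participants will receive beta blockade on the day of the scan". It then requires heart rate and blood pressure to be measured, and says that participants "will be assessed for contraindications to beta blockade (bradycardia, heart block, active wheezing, history of adverse reaction". After dosing: "Vital signs will be obtained and documented following metoprolol administration". There is an alert limit: "If at any time the heart rate is <50 bpm and/or the systolic BP is <100, the supervising physician will be notified". Symptoms of low heart rate or low blood pressure are assessed after the scan.

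The PET exclusions (sections 1.3 and 2.2) concern activity restriction, fasting, diabetes and blood glucose. They name no contraindication to a beta-blocker.

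**The concern.** Metoprolol is given here only to improve a research image. The protocol already recognises, for CT, that some people should not receive it and that those who do should be watched. If the PET sentence is followed literally, a participant who is wheezing, or whose heart rate is already low, would receive at least 50 mg, and nothing in that text tells staff to look first or to hold the dose. The protocol's own drug information (section 10.0) warns of bronchial constriction in people prone to bronchospasm. Severe asthma appears in section 2.2 only as a bar to gadolinium, and those participants may still have the other evaluations.

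What is at stake is participant safety in a pilot substudy. Neither the primary endpoint nor the FDG measurements are in question.

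**Working it through.** No figure in the plan needs to be reproduced. The check compares the two dosing texts, then asks what else in the protocol would act at each PET visit.

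**1. The two dosing texts in section 1.3**

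| Step | CT angiography (Beta Blockade) | PET Substudy |
|---|---|---|
| Heart rate and blood pressure before dosing | Required | Not stated |
| Contraindication check | Required | Not stated |
| Dose decision | "the supervising physician customizes the dose on an individual subject to achieve a goal heart rate of less than 60 beats per minute" | 50-100 mg; no decision-maker and no target rate named |
| Agents and oral range | "A net dose of metoprolol 25-200 mg or atenolol 50-100 mg or diltiazem 90-360 mg" | Metoprolol only, 50-100 mg |
| Vital signs after dosing | Required | Not stated |
| Limits for notifying the physician | Heart rate below 50 or systolic pressure below 100 | Not stated |
| Symptom check after the scan | Required | Not stated |

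The PET text does not refer back to the CT text.

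**2. Month 0**

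Appendix B puts CT angiography and PET in the same visit column, and section 2.1 requires an eGFR above 45, so renal function should seldom rule out the CT. Section 2.3 adds a medical history and physical examination with vital signs. Most PET participants would therefore have a beta-blocker assessment around this visit. Same-day cover is still not assured: section 3.2 allows PET participants 1-3 additional visits, so the PET scan may fall on another day. A participant barred from iodinated contrast may also still have PET (section 2.2).

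**3. Month 6**

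Appendix B marks PET but not CT angiography, which is at months 0 and 24. History and physical is marked at screening and at months 12 and 24, not at month 6. What does take place is an adverse event review, a medication review, safety laboratory tests (section 3.2, Appendix B) and an interim medical history (section 3.2). The only PET-specific safety item in section 3.2 is blood glucose. None of these requires a heart rate, a blood pressure or a contraindication check on the morning of dosing. The CT part of the PET/CT examination is a separate acquisition without intravenous contrast, and its description does not bring in the beta-blockade procedure.

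**4. Number of doses**

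- All PET doses: 60 participants × 2 scans = 120 at most.
- Month-6 doses: 60 × 1 = 60 at most, fewer with dropout.

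These are ceilings on doses given. They do not count unsafe doses. The documents do not say how many participants have a contraindication, so no risk can be calculated.

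**The case against.** The strongest reply is that the safeguards already cover PET. Beta Blockade has its own subheading and speaks of participants and the scan in general terms, whereas the nitrate paragraph that follows limits itself to MDCT. This stands in part. A reader might infer from the layout that the safeguards exclude PET, and the documents do not support that: the wording is ambiguous. But it permits the extension without requiring it. The reproducibility substudy does import the CT methods expressly. That contrast is weak evidence, since the reproducibility scan repeats the same CT examination.

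Other text narrows the gap:

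- Section 2.2 (item I) lets the researcher exclude anyone for whom MRI or CT would be unsafe.
- Section 2.3 provides a baseline history and examination that should reveal standing conditions such as asthma.
- Section 3.2 provides interim reviews at month 6.
- Section 8.1 lists low heart rate and low blood pressure after beta blockade as expected events, without limiting this to CT, which presumes that someone is measuring.

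All of this stands as mitigation, and none of it is a check required just before the month-6 dose. What remains is mainly a condition that is new since baseline or present on the day.

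It is also fair that 50-100 mg leaves some discretion and that clinical staff would be unlikely to dose someone who is visibly wheezing. A reader might infer that PET dosing is the more aggressive of the two. It is not: its range lies inside the 25-200 mg oral metoprolol range allowed for CT.

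Finally, the PET substudy has a separate consent (section 7.5). The consent pages are not in the text available, and precautions could be stated there.

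**Conclusion.** The point holds as a minor participant-safety gap. Section 1.3 directs metoprolol before both PET scans without stating a pre-dose check, a hold rule or post-dose monitoring. At month 6 nothing else in the protocol clearly requires a same-day check. At most 60 doses fall at that visit, out of at most 120.

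It would be wrong to read either number as participants put at risk, or to conclude that doses were in fact given unsafely. The documents describe what was planned and not what staff did.

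The conclusion assumes that the consent form adds no PET-specific precautions and that the month-6 PET scan takes place without a CT angiogram, as Appendix B shows. No effect on any endpoint, on power or on error rates is claimed. Section 7.4 says that the study has been in data analysis only since January 2017, so this is a comment on the protocol as designed. It is a cheap improvement to a 60-person pilot substudy.

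**What to change.** Add two sentences to the PET imaging technique in section 1.3.

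1. The safety steps listed under Beta Blockade apply at each PET scan: heart rate, blood pressure and contraindication check before the dose; vital signs after it, with the physician notified at a heart rate below 50 or a systolic pressure below 100; and a symptom check after the scan.
2. The supervising physician may reduce or omit metoprolol when it is contraindicated or unnecessary, and the scan still goes ahead. The nitrate paragraph offers a model: "If the patient cannot receive nitroglycerine (due to intolerance, borderline blood pressure, investigator judgment), the patient may still proceed with the study".

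The CT titration goal of under 60 beats per minute should not be carried over. The PET text sets no target rate, and the safety steps do not depend on one.

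The cost is brief vital-sign checks at up to 120 scans, and some PET scans acquired without heart-rate control, whose cardiac images may be less sharp.
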